### 11.2.3 Presentation of adverse events

An overview of the number and percentage of subjects who experience TEAEs will be presented based on the SS. This tabulation will include the number and percentage of subjects with any TEAEs, serious TEAEs, related TEAEs, discontinuation due to TEAEs, severe TEAEs, AEs leading to death and TEAEs leading to death; event counts will also be included.

- The tabulation will be presented by PS0018 dose at onset.
- This tabulation will be repeated by Dose adjustment and PS0016 randomized treatment group.

In addition, the following summaries will be presented by PS0018 dose at onset, SOC, high level term (HLT) and PT, based on the SS:

- Incidence of TEAEs by PS0018 dose at onset, including the EAIR and EAER calculated as described in [Section 11.2.2](#) for the 'Any TEAE' category only
- Incidence of TEAEs by PS0018 dose at onset, including the EAIR and EAER calculated as described in [Section 11.2.2](#) for the 'Any TEAE' category only by overall ADA status (positive/negative)
- Incidence of TEAEs by Dose adjustment and PS0016 randomized treatment group
- Incidence of serious TEAEs by PS0018 dose at onset and Dose adjustment
- Incidence of TEAEs by relationship and PS0018 dose at onset
- Incidence of TEAEs by maximum relationship and PS0018 dose at onset
- Incidence of TEAEs by maximum intensity and PS0018 dose at onset
- Incidence of fatal TEAEs by relationship and PS0018 dose at onset

- Incidence of serious TEAEs by relationship and PS0018 dose at onset
- Incidence of non-serious TEAEs above threshold of 5% of subjects by PS0018 dose at onset
- Incidence of non-serious TEAEs above threshold of 5% of subjects by relationship and PS0018 dose at onset
- Incidence of ongoing AEs from PS0016
- Incidence of ongoing AEs from PS0016 which do not worsen in severity, or AEs started prior to PS0018 dose, by PS0016 randomized treatment group

In addition, separate AE summaries by PS0018 dose at onset, SOC, HLT and PT will be included for the following AEs of special monitoring (AESM) further defined in [Section 14.3](#).

- Major cardiovascular events
- Serious infections, including opportunistic infections and tuberculosis (TB)
- Malignancies including lymphoma
- Cytopenias
- Neuropsychiatric events (in particular, depression and suicide)
- Inflammatory bowel disease
- Anaphylactic reaction (hypersensitivity and anaphylactic reactions)
- Hepatic events and drug-induced liver injury

All summary tables (including those for AESM) will contain the number and percentage of subjects and the number of events where applicable. A subject who has multiple events in the same SOC, HLT and PT will be counted only once in the subject counts but all events will be included. In addition, for all tabulations of AESM, the EAER and EAIR will be reported only for the categories 'Any TEAE'.

The criteria for identifying AESM and additional criteria for reporting AESM are provided in [Section 14.3](#).

Adverse event summaries will be ordered by alphabetical SOC, alphabetical HLT within SOC and decreasing frequency of PT in the 'BKZ 320mg' column for the PS0016 randomized treatment group. In the PS0018 dose at onset tables, the summaries will be presented in a similar manner in decreasing frequency of PT in the 'All BKZ' column.

For tables including only number and percentage of subjects, summaries will be ordered by alphabetical SOC, alphabetical HLT within SOC and decreasing incidence of PT within HLT and SOC in the 'All BKZ' column.

Any adverse events considered ongoing from PS0016 which do not worsen in severity during PS0018 dosing, or starting prior to first PS0018 dose will not be considered treatment emergent in PS0018 and will be tabulated separately.

The AEs will be listed by PS0016 randomized treatment group and include all subjects screened in the ES. The listing will include the onset date/time and outcome date/time of the event (including relative days), the AE duration (derived), dose at onset, days since first dose of study

medication, days since most recent dose of study medication, pattern of event, intensity, relationship, action taken and outcome. In addition the listing will flag AEs that led to discontinuation, TEAEs, AESM, AEs of special interest (as reported on the eCRF) and SAEs.

A glossary of all TEAE terms will be provided including the SOC, HLT, PT and reported term.

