#### **3.2 Secondary objectives**

Secondary objectives of the study are:

- To assess the safety and tolerability of increasing the dose of bimekizumab from 160mg Q4W to 320mg Q4W for subjects with an inadequate response at Week 12
- To assess PK of bimekizumab
- To assess the immunogenicity of bimekizumab
- To assess the efficacy of open-label bimekizumab 160mg Q4W administered over 48 weeks

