#### **14.2.1 Primary safety analysis**

All TEAEs will be summarized descriptively by treatment group, primary system or organ class (SOC), high level term (HLT), and preferred term (PT). This summary will include the exposure adjusted incidence rate (EAIR) with associated 95% confidence interval and the exposure adjusted event rate (EAER).

For EAIR, the numerator will be the total number of subjects experiencing the AE. The denominator will be 100 subject-years; that is, the total summation of individual subject-years at risk up to the first occurrence of the AE for subjects with that AE, and the total subject-years at risk for those subjects not experiencing that AE, divided by 100. Exposure adjusted incidence rates will be presented with a 95% exact confidence interval based upon the Chi-Square distribution (Ulm, 1990).

For EAERs, the numerator will be the number of AEs including repeat occurrences in individual subjects; the denominator will be 100 subject-years. That is, the total summation of individual subject-years at risk divided by 100. No confidence interval will be computed for EAER.

Subject exposure at risk in days will be defined as date of last administration of study medication – date of first administration of study medication +140 days (ie, the duration of the SFU Period). If a subject dies, patient exposure at risk is censored at the date of death. The sum of these exposure days at risk across subjects is converted to years for the EAIR and EAER calculations described above.

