### **3.9 Changes to protocol-defined analyses**

Change from Baseline in physical examination is listed as a secondary safety variable, in [Section 2.2.1.2](#). Only whether the physical examination was performed and the date it was performed is recorded on the CRF. Thus no summaries for the change from Baseline in physical examination will be provided.”

For the continuous efficacy variables based on the change from Baseline (PASI, BSA, and HADS), imputation for missing values in the protocol is based on multiple imputation (MI) via the Markov Chain Monte Carlo (MCMC) method. However, due to the smaller sample size in PS0018 this may cause problems in the algorithm. For this reason and for consistency with the PS0016 SAP, imputation in PS0018 will instead be based on last observation carried forward (LOCF).

For the dose adjustment groupings, the single and multiple dose adjuster groupings will be combined for summary purposes, unless stated otherwise.

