### 11.1 Extent of exposure

#### 11.1.1 Drug administration

All drug administration details (including date, time of injection, location, side of body and volume delivered) will be listed by subject and visit. The study medication will be given as 1 or 2 sc injections depending on dose, at each planned dosing visit (PS0018 Week 0, Weeks 4, 8, 12, 16, 20, 24, 28, 32, 40 and Week 44).

The duration of exposure (in days) will be calculated as:

$$\text{Date of last dose in PS0018} - \text{Date of first dose in PS0018} + 28 \quad [10]$$

Should the date of the last dose plus 28 days equate to a date that is beyond the Week 48 visit date then the exposure will be calculated as:

$$\text{Week 48 visit date} - \text{Date of first dose in PS0018} + 1 \quad [11]$$

For subjects who have died the exposure will be as follows:

$$\text{Date of death} - \text{Date of first dose in PS0018} + 1 \quad [12]$$

For subjects who switched dose during PS0018, the duration of dose within each dose interval (except the last dose interval) will be calculated as:

$$\text{Date of last dose in PS0018} - \text{Date of first dose in PS0018} + 1 \quad [13]$$

The dose taken in the last dose interval will be calculated as:

$$\text{Date of last dose in PS0018} - \text{Date of first dose in PS0018} + 28 \quad [14]$$

In this case duration of exposure will be calculated as the sum of the dose intervals for bimekizumab 160mg Q4W and 320mg Q4W, respectively.

Extent of exposure in PS0018 will be summarized using descriptive statistics and presented by bimekizumab 160mg Q4W, 320mg Q4W, respectively and All bimekizumab.

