#### 11.1.2 Subject time at risk

The subject time at risk represents the time a subject was at risk for having an AE and will be used to calculate the exposure adjusted incidence rate (EAIR) and exposure adjusted event rate (EAER) as described in [Section 11.2.2](#).

The subject time at risk (days) will be calculated as follows:

$$\text{Time at risk} = (\text{Date of Last PS0018 IMP} - \text{Date of First PS0018 IMP}) + 140 \quad [15]$$

This includes the duration of the SFU Period.

For subjects who switch dose during PS0018, time at risk will be derived in each dose interval and calculated as per equation [13] above, and equation [15] will be applied for the dose in the final dose interval.

In cases where the last clinical contact or last visit occurs prior to completion of the SFU period, the subject time at risk is calculated as follows:

$$\text{Time at Risk} = (\text{Date of Last Contact} - \text{Date of First PS0018 IMP}) + 1 \quad [16]$$

This will apply for the following:

- For subjects that discontinue prematurely (ie, and no SFU data are available), the date of final contact refers to the date of the latest contact with the subject during the study PS0018 after which no further information or data are available. This will be reported on the study termination page of the electronic Case Report Form (eCRF).
- For subjects that have died during the study the date of last contact refers to the date of death

The sum of these exposure days at risk across subjects in the relevant PS0018 dose group is converted to years for the EAIR and EAER calculations described in [Section 11.2.2](#).

Subject-years at risk is defined as the subject time (in days) at risk divided by 365.25. The days at risk and subject years at risk will be listed and summed by PS0018 dose at onset, together with the drug administration information ([Section 11.1.1](#)).

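### SAP 11.2.3 gives exposure-adjusted rates for 'Any TEAE' only, an undeclared change from protocol 14.2.1, and SAP 11.1.2 drops about 27 days of time at risk before each dose switch

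*SAP*

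**What the plan says.** **Protocol.** The primary safety variable (4.1.1) is TEAE incidence adjusted for duration of exposure. Section 14.2.1 summarizes all TEAEs by treatment group, SOC, HLT and PT, and continues: "This summary will include the exposure adjusted incidence rate (EAIR) with associated 95% confidence interval and the exposure adjusted event rate (EAER"). The EAIR denominator is specific to the event: "the total summation of individual subject-years at risk up to the first occurrence of the AE for subjects with that AE", plus full time at risk for subjects without it. Time at risk is last dose minus first dose plus 140 days. A secondary objective (3.2) is "To assess the safety and tolerability of increasing the dose of bimekizumab from 160mg Q4W to 320mg Q4W" in subjects with an inadequate response at Week 12; section 5.1 allows the increase at Week 12 or later.

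**SAP, presentation.** Section 11.2.2 defines the EAIR for a specific TEAE, with an exact Poisson interval. Section 11.2.3 then gives EAIR and EAER in the SOC/HLT/PT table by dose at onset "for the 'Any TEAE' category only". Sections 11.2.3 and 14.3 also limit the special-monitoring (AESM) tables to overall-row rates. Section 3.9 declares three changes: no physical-examination summaries, LOCF in place of multiple imputation, and a merger of adjuster groups ("For the dose adjustment groupings, the single and multiple dose adjuster groupings will be combined for summary purposes, unless stated otherwise"). The rate restriction is not among them, and the SAP amendment list does not mention it.

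**SAP, time at risk.** For subjects who switch dose, 11.1.1 introduces equation [13] with "the duration of dose within each dose interval (except the last dose interval) will be calculated as" last dose minus first dose plus 1. Section 11.1.2 reuses it: "time at risk will be derived in each dose interval and calculated as per equation [13] above", with [15] (plus 140 days) for the final interval. Section 11.2.1 attributes each TEAE to the last dose being received at onset.

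**The concern.** There are two problems.

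First, the event-specific denominator in protocol 14.2.1 makes sense only if a rate is shown for each event row. SAP 11.2.2 keeps that definition, but 11.2.3 uses it for one row, without a stated reason and without an entry in 3.9. The other rows then show counts and crude percentages. All subjects start on 160 mg and some move to 320 mg, so the two dose columns have unequal time at risk. A crude percentage ignores this, in the table meant to inform on the safety of the dose increase.

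Second, the numerator and denominator of the by-dose rates follow different clocks. An event that starts after the last 160 mg injection but before the first 320 mg injection counts as a 160 mg event, yet most of those days are in nobody's denominator. This affects the 'Any TEAE' rate by dose that is already planned, whatever is decided about the rows.

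**Working it through.** The documents give no figure for either point and do not say how many subjects switch or when. The numbers below are therefore scenarios.

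**Inputs.** Planned N = 45 (protocol 14.7). Injections every 4 weeks from Week 0 to Week 44, so a completer's last dose is day 44 × 7 = 308. Time at risk per protocol 14.2.1: 308 + 140 = 448 days.

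**Assumptions.** All 45 complete; k = 5, 10 or 15 switch up once, all at week w; the true rate r is the same on both doses; column percentages use subjects who received that dose (SAP 3.1 gives only a general denominator rule). Equations [13] and [15] are read within each dose interval.

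**1. Effect of equation [13] on one Week 12 switcher.**
- Last 160 mg injection: Week 8, day 56. Under [13]: 56 − 0 + 1 = 57 days.
- First 320 mg injection: day 84. Days on 160 mg: 84. Gap: 84 − 57 = 27 days.
- Final interval under [15]: (308 − 84) + 140 = 364 days.
- SAP total: 57 + 364 = 421 days. Protocol total: 448 days.

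**2. Effect on the 160 mg rate, all switches at Week 12.** The denominator in days is (45 − k) × 448 + k × 84 for the full interval, and (45 − k) × 448 + k × 57 under [13].

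| k | Full interval | Under [13] | Rate inflated by |
|---|---|---|---|
| 5 | 18,340 d (50.21 y) | 18,205 d (49.84 y) | 0.7% |
| 10 | 16,520 d (45.23 y) | 16,250 d (44.49 y) | 1.7% |
| 15 | 14,700 d (40.25 y) | 14,295 d (39.14 y) | 2.8% |

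**3. Effect on the 320 mg rate.** If nobody returns to 160 mg, the 320 mg interval is final and [13] does not touch it: 0%. If 10 switch up at Week 12 and 5 return at Week 24, each returner has 57 instead of 84 days on 320 mg. The denominators are 5 × 364 + 5 × 84 = 2,240 days and 5 × 364 + 5 × 57 = 2,105 days; 2,240 / 2,105 = 1.064, an inflation of 6.4%.

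**4. Distortion in crude row percentages.** With p(d) = 1 − exp(−r·d/365.25), the expected 160 mg percentage is [(45 − k)·p(448) + k·p(7w)]/45 and the 320 mg percentage is p(448 − 7w). The 160:320 ratio should be 1 when the true rates are equal. At r = 0.3 events per subject-year:

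| Switch week | k = 5 | k = 10 | k = 15 |
|---|---|---|---|
| 12 | 1.09 | 0.98 | 0.88 |
| 24 | 1.40 | 1.30 | 1.21 |

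Over r = 0.1 to 1.0 the ranges are 0.86 to 1.11 (Week 12) and 1.11 to 1.46 (Week 24). If 9 non-switchers instead leave at Week 12 after a last dose at Week 8 (56 + 140 = 196 days at risk), the ranges at r = 0.3 are 0.76 to 0.96 and 1.05 to 1.25.

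**5. What row-level intervals would look like.** With equation [18], 15 subjects in 40 subject-years give 37.5 per 100 (95% CI 21.0 to 61.9); 2 subjects in 4.83 subject-years give 41.4 (5.0 to 150).

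**The case against.** The strongest reply is that this is mostly a documentation gap. SAP section 1 lets the SAP depart from the protocol where its sections say so, and 11.2.3 says so openly. The primary variable is still delivered as an exposure-adjusted rate by dose. The AESM tables carry EAIR and EAER in their overall rows, so several safety topics have rates. Row-level EAER is not lost either: its denominator is the same for every row, so it follows from the printed event counts and the summed subject-years. Only the row-level EAIR needs the listings, and in sparse rows it would be very imprecise. All of this stands. It limits the weight of the point but does not remove the mismatch with 14.2.1 or the silence of 3.9.

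A reader might infer more than the documents support:

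- *That the primary analysis has been dropped.* It has not; the 'Any TEAE' rate by dose remains.
- *That crude percentages mislead by about twofold.* That needs every switcher to move at Week 36 (ratio 1.80 to 1.98 at r = 0.3). Nothing in the documents suggests it, and the secondary objective is framed around inadequate response at Week 12.
- *That the 320 mg rate is inflated by nearly half.* The 47% figure arises only if all 10 of 10 switchers return to 160 mg at Week 24 (840 against 570 days).
- *That 11.2.2 puts 160 mg time into the 320 mg EAIR, because it starts the clock for event subjects at the first PS0018 dose.* Equation [13] uses the same phrase as shorthand within a dose interval, and 11.2.2 refers to subjects at risk in each dose group. It is probably loose wording and calls for clarification only.
- *That serious infections go unreported.* SAP 14.3.2.1 places them in the SAE tables, and fungal and opportunistic infections have their own. The mismatch with the AESM lists in 11.2.3 and 14.3 is a separate minor item.

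**Conclusion.** Both parts hold at moderate weight. The restriction to 'Any TEAE' is an undeclared and unexplained departure from the primary safety summary; its main cost is the row-level EAIR with its interval. Under the equal-rate scenarios for completers, crude percentages do little harm if switches occur at Week 12 (ratio about 0.9 to 1.1 at 0.3 events per subject-year) and more if they come later (about 1.2 to 1.4 at Week 24).

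The time-at-risk rule is wrong as written: events are counted in days that the denominator omits, and a switcher's intervals sum to 421 days against the protocol's 448. The effect is small: 0.7 to 2.8% on the 160 mg rate for 5 to 15 Week 12 switchers among 45 completers, none on the 320 mg rate unless subjects step back down, and about 6% if 5 of 10 return at Week 24.

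The text findings do not depend on these scenarios; the sizes do. Exposure adjustment would not make the dose columns comparable in other respects, because the 320 mg group is selected for inadequate response.

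**What to change.** 1. **SAP 11.2.3, or 3.9.** In the main dose-at-onset table, give EAIR with exact 95% CI and EAER for Any TEAE and for each SOC, HLT and PT. If the sponsor prefers the restriction, declare it in 3.9 with the reason.
2. **SAP 11.1.2, time at risk by dose.** Replace [13]: a non-final interval runs from its first injection to the day before the first injection of the next dose. [15] applies to the final interval, counted from that interval's first injection. [16] must be counted from the same point; it now counts from the first PS0018 dose, so a switcher with an early last contact would have the 160 mg days counted twice. The 'All BKZ' column keeps [15] and [16] from the first PS0018 dose.
3. **SAP 11.2.2, clarification.** In the 160 mg and 320 mg columns, time to first event is time on that dose only, adding earlier intervals on the same dose. In 'All BKZ' it runs from the first PS0018 dose. A TEAE on the switch day that 11.2.1 assigns to the earlier dose is counted to the end of that interval.

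Cost: a wider table, very wide intervals in sparse rows, and minor reprogramming. No new data are needed.

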**Table 5–1: Schedule of study assessments**

Protocol activity	Visit Week a PS0018 Baseline	Open-Label Treatment Period													SFU b
		Wk 4	Wk 8	Wk 12	Wk 16	Wk 20	Wk 24	Wk 28	Wk 32	Wk 36	Wk 40	Wk 44	Wk 48/ WD		
Informed consent	X c														
Inclusion/exclusion	X d														
Physical exam e	X f												X	X	
Body weight	X f												X	X	
Vital signs g	X f	X	X	X	X	X	X	X	X	X	X	X	X	X	
Hematology/biochemistry/urinalysis h	X f		X		X		X		X		X		X	X	
12-lead ECG	X f						X						X	X	
Pregnancy testing i	X	X	X	X	X	X	X	X	X	X	X	X	X	X	
C-SSRS	X f	X	X	X	X	X	X	X	X	X	X	X	X	X	
IGRA TB test j	X f												X	X	
TB questionnaire	X f			X			X			X			X		
Blood sample for bimekizumab plasma concentrations k	X f	X	X	X	X			X			X		X	X	
Blood sample for anti-bimekizumab antibodies k	X f	X	X	X	X			X			X		X	X	
PASI	X f	X	X	X	X	X	X	X	X	X	X	X	X	X	
IGA	X f	X	X	X	X	X	X	X	X	X	X	X	X	X	
BSA	X f	X	X	X	X	X	X	X	X	X	X	X	X		
HADS	X f			X			X			X			X		
Concomitant medications	X	X	X	X	X	X	X	X	X	X	X	X	X	X	
Adverse events	X	X	X	X	X	X	X	X	X	X	X	X	X	X l	
IXRS	X	X	X	X	X	X	X	X	X	X	X	X			
Bimekizumab administration m, n	X	X	X	X m	X m	X m	X m	X m	X m	X m	X m	X m			

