## 10 IMMUNOLOGY

The results for the anti-drug (bimekizumab) antibody (ADA) measurements will be listed by PS0016 randomized treatment group and timepoint based on the SS, including the screening assay, confirmatory assay and titer (if applicable).

A cut point will be determined by the bioanalytical laboratory that will be used to determine the status of ADA as above the cut point (ACP) or below the cut point (BCP). For any ADA levels that are ACP, a further confirmatory assay will be performed, the results of which will be determined as either 'confirmed positive' (CP) or 'not confirmed positive' (NCP). For samples that are CP, a further titer assay will be performed and the ADA titer will be reported.

The following definitions will be applied 2 ways: firstly including the PS0018 SFU visit, and then excluding the PS0018 SFU visit:

- An ADA status of positive will be concluded for any subject with an ADA level that is ACP and CP at any timepoint (PS0016 Baseline, Week 4 and Week 8, and all PS0018 visits)
- An ADA status of negative will be concluded for any subject with an ADA level that is either BCP or ACP and NCP at any timepoint (PS0016 Baseline, Week 4 and Week 8, and all PS0018 visits)
- A subject will be classified as having ADA positivity at PS0016 Baseline if the PS0016 Day 1, predose result is ACP and CP
- A subject will be classified as having treatment-induced ADA positivity when meeting one of the following criteria:
  - The PS0016 Baseline result is either BCP or ACP and NCP, and at least one PS0018 timepoint is ACP and CP
  - The PS0016 Baseline result is positive (ACP and CP) and at least one PS0018 measurement shows a pre-defined fold increase in titer from the Baseline value (the fold increase from PS0016 Baseline required to meet this criteria will be defined with the development of the assay and will be included in the TFLs)
- A subject will be classified as overall positive if at least one PS0018 measurement is ACP and CP (this includes subjects who have negative results at Baseline)
- A subject will be classified as overall negative if at all PS0018 visits the ADA status is negative (this includes subjects who have positive [ACP and CP] results at Baseline)

All listings, summaries and figures will include the PS0016 visits Baseline, Week 4 and Week 8 and all PS0018 visits.

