### 11.2.2 Calculation of exposure adjusted incidence and event rates

The EAIR is defined as the number of subjects (n) with a specific TEAE adjusted for the exposure and will be scaled to 100 subject years:

$$EAIR = 100 \times \frac{n}{\sum_{i=1}^N TExp,i} \quad [17]$$

In the above equation, N is the total number of subjects at risk (in each PS0018 dose group) and TExp,i is the time at risk for subject i, expressed in years. Subject time at risk represents the time a subject was at risk for having a TEAE calculated as follows:

- For subjects experiencing the specific TEAE the time at risk (TExp,i) is calculated from the time of the first PS0018 dose to the onset of the TEAE. If a subject has multiple events, the time at risk is calculated relative to the first occurrence of the TEAE being considered.
- For subjects who do not experience the specific TEAE the total time at risk (TExp,i) is calculated as described in [Section 11.1.2](#).

Exact Poisson 95% CIs (lower confidence limit [LCL], upper confidence limit [UCL]) for the EAIR will be calculated using the relationship between the Poisson and the chi-square distribution (Ulm, 1990; Fay and Feuer, 1997):

$$LCL = \frac{\chi_{2n, \frac{\alpha}{2}}^2}{2}, UCL = \frac{\chi_{2(n+1), 1 - \frac{\alpha}{2}}^2}{2} \quad [18]$$

where n is the number of subjects with the specific TEAE for the incidence rate of interest and is the basis for the number of the degrees of freedom for the chi-square quantile. The LCL and UCL calculated above will be scaled to the number of subject years by dividing these by the total exposure at risk for each treatment group ( $\sum_{i=1}^N \text{TExp}, i$ ).

The EAER is defined as the total number of TEAEs (including repeat occurrences in individual subjects) divided by the total time at risk scaled to 100 subject years:

$$EAER = 100 \times \frac{n_{AE}}{\sum_{i=1}^N \text{TRisk}, i} \quad [19]$$

where  $n_{AE}$  is the total number of TEAEs and  $\text{TRisk}, i$  is the time at risk for subject i, expressed in years (calculated as described in [Section 11.1.2](#)).

No CIs will be computed for EAER.

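### The TEAE table by overall ADA status counts events and time before first antibody detection as ADA-positive, which dilutes any real ADA effect and loses the time order

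*SAP*

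**What the plan says.** SAP 11.2.3 lists a TEAE summary by PS0018 dose at onset in which EAIR and EAER are given for the any-TEAE "category only by overall ADA status (positive/negative".

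SAP 10 defines the two groups. "A subject will be classified as overall positive if at least one PS0018 measurement is ACP and CP", that is, above the assay cut point and confirmed. Conversely, "A subject will be classified as overall negative if at all PS0018 visits the ADA status is negative". These definitions are applied in two versions, "firstly including the PS0018 SFU visit, and then excluding the PS0018 SFU visit". Section 11.2.3 does not say which version its table uses.

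SAP 11.2.2 sets the EAIR clock. For a subject with the event, "the time at risk (TExp,i) is calculated from the time of the first PS0018 dose to the onset of the TEAE". "For subjects who do not experience the specific TEAE the total time at risk (TExp,i) is calculated as described in" Section 11.1.2, which runs to the last dose plus 140 days. The EAER uses that full time for every subject. The only planned division of events and time is by dose.

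Protocol Table 5–1, in the row "Blood sample for anti-bimekizumab antibodies", schedules samples at Baseline (Week 0), Weeks 4, 8, 12, 16, 28, 40 and 48/withdrawal, and at the SFU Visit.

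**The concern.** ADA status can change during the study, but this table treats it as a fixed attribute that later data may determine. A subject first positive at Week 28 has every TEAE from Week 0 onward placed in the ADA-positive column, with the matching time. In the version that includes the SFU sample, a subject positive only at SFU has all TEAEs reported as ADA-positive, although none followed a positive result.

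This is the only planned summary that joins immunogenicity (a secondary objective) to adverse events. Its natural use is to ask whether antibody-positive subjects have more events once antibodies are present. Mixing pre-detection and post-detection experience pulls the two columns together, so a real effect would look smaller than it is. The SAP already applies the relevant principle to dose, since TEAEs go to the dose at onset and time is split by dose interval.

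**Working it through.** **Reproducing the plan's figure.** SAP 11.1.2 defines time at risk as (last dose − first dose) + 140 days. With the last dose at Week 44 (SAP 3.2.1.2), this is 308 + 140 = 448 days = 64 weeks = 1.227 years, which matches the stated maximum of 64 weeks.

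**Share of EAER time before detection.** For a completer, f = day of first positive sample / 448.

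**Expected EAER ratio.** The documents give no ADA effect, so a true rate ratio RR of 1.5 to 3 after conversion is assumed, with conversion taken at detection. A converter's observed EAER relative to an ADA-negative subject is f + (1 − f) × RR. For Week 28 and RR = 2: 0.4375 + 0.5625 × 2 = 1.56.

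| First positive | f | RR 1.5 | RR 2 | RR 3 |
|---|---|---|---|---|
| Week 0 | 0/448 = 0% | 1.50 | 2.00 | 3.00 |
| Week 4 | 28/448 = 6.25% | 1.47 | 1.94 | 2.88 |
| Week 8 | 56/448 = 12.5% | 1.44 | 1.88 | 2.75 |
| Week 12 | 84/448 = 18.75% | 1.41 | 1.81 | 2.63 |
| Week 16 | 112/448 = 25% | 1.38 | 1.75 | 2.50 |
| Week 28 | 196/448 = 43.75% | 1.28 | 1.56 | 2.13 |
| Week 40 | 280/448 = 62.5% | 1.19 | 1.38 | 1.75 |
| Week 48 | 336/448 = 75% | 1.13 | 1.25 | 1.50 |
| SFU (SFU-inclusive version only) | 448/448 = 100% | 1.00 | 1.00 | 1.00 |

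**EAIR.** These shares do not describe the EAIR of a subject with an event, because the clock stops at the first TEAE. The question there is whether that TEAE came before detection, with probability 1 − exp(−rate × time). For a first positive at Week 28 (196/365.25 = 0.537 years) and assumed rates of 1, 2 and 3 TEAEs per subject-year, the probability is 42%, 66% and 80%.

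**Simulation.** 40,000 subjects were simulated on the Table 5–1 sampling schedule, assuming 2 TEAEs and 0.5 conversions per subject-year. Rates are per 100 subject-years, ADA-positive versus ADA-negative.

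- True RR of 2, no dropout. SAP grouping: EAER 311.5 vs 198.7 (ratio 1.57) and EAIR 248.9 vs 200.6 (ratio 1.24). Split at the first positive sample: EAER 401.8 vs 208.0 (ratio 1.93; short of 2 because detection lags conversion).
- No ADA effect, no dropout. SAP grouping: EAER 199.5 vs 200.4.
- No ADA effect, dropout unrelated to TEAEs. SAP grouping: EAER 199.6 vs 199.7.
- No ADA effect, 10% of on-treatment TEAEs ending participation with no further samples. SAP grouping: EAER 190.5 vs 208.1 (ratio 0.92) and EAIR 184.9 vs 209.6 (ratio 0.88). Split: EAER 199.4 vs 200.6 (ratio 0.99).

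**The case against.** A reader might infer that the ADA-positive column gains event-free time by construction, and so is biased even when antibodies do nothing. The documents do not support that. A TEAE does not end follow-up, and pre-detection events are counted together with pre-detection time. The simulation is near null without an ADA effect, even with dropout, provided the dropout is unrelated to TEAEs. A spurious difference needs follow-up linked to AEs, or a TEAE rate that changes over time together with unequal follow-up. Protocol 6.3 does link withdrawal to AEs and laboratory values, but the 10% above is an assumption.

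A reader might also infer that early withdrawals drift into the negative column for want of samples. They do give fewer samples, but the withdrawal and SFU visits both include an ADA sample (Protocol 8.9 to 8.11). SAP 4.4 also assigns withdrawal-visit ADA results to the next ADA visit so that positivity is not lost. The simulated dropout gave no such samples, so that scenario is harsher than the plan.

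It is also fair to say that the table is not central. Protocol 14.4 asks only for ADA summaries by treatment and visit, and the TEAE-by-ADA table is a descriptive addition. SAP 10 tabulates the first occurrence of treatment-induced positivity and provides ADA listings and subject plots, and the AE listing gives onset days. With at most 45 subjects, the sequence could be pieced together by hand. Some subjects may already be positive at Week 0 after dosing in PS0016 and would then have no misattributed time.

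These points limit the importance. They do not restore the time order, because no planned output sets TEAE onset beside ADA timing, and the dilution remains.

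**Conclusion.** The point holds as a limitation of one supportive table. For subjects who convert after Week 0, the table assigns pre-detection TEAEs and time to the ADA-positive group. In a completer, 6% to 75% of EAER time is affected for a first positive between Weeks 4 and 48, and 100% for a first positive at SFU if that sample counts. The certain consequences are loss of the order between antibody and event and, if antibodies do affect TEAEs, an understated effect. With a true doubling, the EAER ratio is 1.56 for a Week 28 converter and 1.25 for a Week 48 converter.

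The shares follow from the documents. The ratios rest on the assumed RR, and the simulated figures also rest on the assumed TEAE and conversion rates. The number of subjects who will convert, and when, is not given. A reader might take this as a flaw in the primary safety analysis, but it is not: the EAIR by dose at onset does not use ADA status.

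**What to change.** In SAP 11.2.3, add a TEAE table by ADA status at onset, with these rules:

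- Events and time are ADA-negative until the first PS0018 sample that is above the cut point and confirmed positive, and ADA-positive from that sample onward.
- A subject positive at PS0018 Week 0 is positive from the first dose.
- For the EAIR, count the first TEAE within each ADA interval, with time at risk starting at the beginning of that interval. A subject may then contribute to both columns.
- For the EAER, use all events and all time in the interval.
- Present the table for All BKZ only, so that cells are not divided again by dose.

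Keep the overall-status table as supportive, and state whether it includes the SFU sample.

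The cost is SAP wording and one more programmed table with interval-level derivations; sample dates and AE onset dates are already collected. Conversion is known only to the nearest sampling visit, with gaps of up to 12 weeks on treatment and 16 weeks from Week 48 to SFU. Some events after true onset will therefore still fall in the negative interval. With at most 45 subjects, the cells will be small.
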